5.2 Sorafenib Tosylate (Nexavar™)

Please refer to the FDA-approved package insert for Nexavar™ for product information, extensive preparation instructions and a comprehensive list of adverse events.

Active Ingredient

Chemical Name: 4-(4-{3-[4-Chloro-3-(trifluoromethyl)phenyl]ureido}phenoxy)N2-methylpyridine-2-carboxamide 4-methylbenzenesulfonate

Trade Name: Nexavar™

Empirical Formula: C₂₁H₁₆ClF₃N₄O₃ x C₇H₈O₃S

Relative Molecular Weight: 637.0

Physical Properties: Insoluble in aqueous media
Slightly soluble in ethanol
Soluble in PEG 400

Finished Product

Presentation and Composition

Nexavar™ contains sorafenib tosylate (274 mg) equivalent to 200 mg of sorafenib and the following inactive ingredients: croscarmellose sodium, microcrystalline cellulose, hypromellose, sodium lauryl sulphate, magnesium stearate, polyethylene glycol, titanium dioxide and ferric oxide red.

Nexavar™ tablets are supplied as round, biconvex, red film-coated tablets, debossed with the “Bayer cross” on one side and “200” on the other side, each containing sorafenib tosylate equivalent to 200 mg of sorafenib.

Storage

Store at 25°C (77°F); excursions permitted to 15-30°C (59-86°F) (see USP controlled room temperature). Store in a dry place.

Availability

Nexavar™ tablets are manufactured by Bayer Healthcare Systems and are commercially available.

Administration

Nexavar™ tablets will be administered orally, as outlined in sections 4.2.1 and 4.2.2.

6.0 CRITERIA FOR SUBJECT ELIGIBILITY

6.1 Subject Inclusion Criteria

1. Patients must have a diagnosis of hepatocellular carcinoma by at least one criterion listed below:
 - a. Histologically confirmed hepatocellular carcinoma
 - b. Axial imaging consistent with liver cirrhosis and at least one solid liver lesion ≥ 2 cm with early enhancement and delayed enhancement washout regardless of alpha-fetoprotein (AFP) levels.
 - c. AFP ≥ 400 ng/ml and evidence of at least one solid liver lesion ≥ 2 cm regardless of specific imaging characteristics.
2. Locally advanced or metastatic disease.
 - a. Patients with locally advanced disease must have disease deemed to be unresectable or not eligible for hepatic transplantation surgical oncologist or transplant physician.
 - b. Measurable disease, as defined as lesions that can accurately be measured in at least one dimension (longest diameter to be

measured) according to Response Evaluation Criteria in Solid Tumors (RECIST, version 1.1) at least 2 cm with conventional techniques or at least 1 cm with spiral computed tomography.

3. Child-Pugh Score A or B7.
4. Age \geq 18 years.
5. Eastern Cooperative Oncology Group (ECOG) Performance Score of 0-2.
6. Absolute neutrophil count \geq 1,200 cells/mm³.
7. Platelet count \geq 70,000 cells/mm³.
8. Total bilirubin \leq 3.0 mg/dl.
9. Hemoglobin \geq 8.5 g/dl.
10. INR \leq 1.8 (therapeutic anticoagulation allowed as long as medically indicated.)
11. Creatinine \leq 1.5 times upper limit of normal.
12. Women of childbearing potential must have a negative pregnancy test.
13. No clinically significant episode of gastrointestinal bleeding within the previous 30 days.
14. Men and women of childbearing potential must be willing to consent to using effective contraception while on treatment and for at least 3 months thereafter.
15. At least 4 weeks since prior locoregional therapy including surgical resection, radiotherapy, hepatic arterial embolization or chemoembolization, radiofrequency ablation, percutaneous injection or cryoablation (treatment of target lesion only, non-target lesions can be treated with locoregional therapy). Provided the target lesion increased in size by 25% or more or the target lesion was not treated with locoregional therapy.
16. Greater than 4 weeks since prior interferon therapy.
17. Greater than 4 weeks since prior and no concurrent use of rifampin or St John's wort.
18. Prior antiviral therapy is allowed.
19. Life expectancy $>$ 12 weeks.
20. Ability to understand informed consent and signing of written informed consent prior to initiation of protocol therapy.
21. Non-English speaking patients will be enrolled.

6.2 Subject Exclusion Criteria

1. History of bleeding diathesis or coagulopathy.
2. Symptomatic or clinically active brain metastases.
3. Major surgery within previous 4 weeks.
4. Clinically significant non-gastrointestinal bleeding within previous 12 months.
5. Concurrent hormone therapy (including hormone replacement therapy and anti-estrogen).
6. History of any condition requiring anti-platelet therapy with the exception of general cardiovascular prophylaxis with aspirin.
7. History of thromboembolic events (including both pulmonary embolisms and deep vein thrombosis but not including tumor thrombus)
8. Active infection
9. Patients who are pregnant or lactating.

10. Hypersensitivity to IV contrast not suitable for pre-medication.
11. Patients with known hypersensitivity to any of the components of bavituximab or sorafenib.
12. Any other medical condition, including mental illness or substance abuse deemed by the investigators to likely interfere with a patient's ability to sign informed consent, cooperate and participate in the study or follow-up procedures.
13. Patients with human immunodeficiency virus (HIV).
14. Significant history of cardiac diseases, including any of the following:
 - a. LVEF < 40% by MUGA or myocardial scintigram.
 - b. NYHA class III-IV congestive heart failure.
 - c. Myocardial infarction within previous 6 months.
 - d. Cardiac arrhythmias requiring anti-arrhythmic therapy (other than beta blockers or digoxin)
15. Evidence of poorly controlled hypertension (medically controlled hypertension is allowed provided blood pressure \leq 150/90.)
16. History of liver or renal transplantation.
17. Prior adjuvant therapy with sorafenib or other Raf/MEK/RAS or VEGFR inhibitors. Prior adjuvant therapy is allowed provided it was completed > 6 months ago and there is documented recurrence of hepatocellular carcinoma.

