The lack of appropriate traditional chemotherapeutic agents led to the investigation of molecular targeted agents, which have been shown to be efficacious in other tumor models. Sorafenib, an oral multikinase inhibitor that blocks tumor cell proliferation by targeting the Raf/MEK/ERK signaling pathway and exerts an anti-angiogenic effect by targeting the tyrosine kinase receptors, VEGFR-2, VEGFR-3 and PDGF- β , is the first biologically targeted agent to show efficacy in the treatment of advanced stage HCC. (13,14) In a phase III randomized controlled trial (SHARP trial), patients with advanced hepatocellular carcinoma (not eligible for surgical resection or transplantation) and preserved liver function (Child-Pugh A score) were randomly assigned to either systemic sorafenib or placebo. There was a significantly longer survival and radiologic time to progression (TTP) outcome in the cohort of patients that received sorafenib with little or no toxicity. Grade 3 drug related events included diarrhea (8% in the sorafenib group vs. 2% in the placebo group), hand-foot skin reaction (8% vs. 1%), hypertension (2% vs. 1%) and abdominal pain (2% vs. 1%); there were no grade 4 drug-related adverse events in any of these categories in either study group. Currently sorafenib is the only drug that has FDA approval for the systemic treatment of HCC. Although sorafenib is the current standard of care for patients with advanced HCC, it prolonged radiologic time to progression less than 3 months when compared to best supportive care: 5.5 months versus 2.8 months, respectively. Overall survival was prolonged less than 3 months compared to best supportive care, 10.7 months versus 7.9 months, respectively. (14) Although systemic treatment with sorafenib shows statistically significant clinical efficacy, its overall benefit is modest. The complexity of HCC would appear to lend itself to escape mechanisms from the sorafenib-specific blockade of the RAF-MEK-ERK and VEGFR/PDGF pathways, thereby promoting tumor proliferation and neo-angiogenesis through alternative means. Such a mechanism would explain why certain patients fail to benefit from sorafenib therapy and provides the rationale for combining sorafenib with other chemotherapeutic agents.

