15.1 Sample size calculation

The phase I component of the study will consist of a traditional 3+3 dose escalation rule with 3 or 6 patients in each cohort, the process for dose escalation is outlined in section 4.1.

The median TTP of patients with advanced HCC treated with sorafenib therapy is 5.5 months. Using this as a benchmark, we will enroll 38 patients, which will allow us to differentiate between a median TTP of 5.5 months and 8.3 months with 80% power and a two-sided significance level of 10% assuming a 24-month accrual and a 12-month follow-up period. TTP will be calculated from initiation of therapy to disease progression (intention to treat) as outlined in section 13.0. Removal from study as outlined in section 14 will be a censored event.

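### Exclusion 17 bars prior sorafenib only when given as adjuvant therapy, so patients pretreated for advanced disease can enter Phase II and be read against a 5.5-month benchmark that probably does not describe them

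*Combined protocol and SAP*

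**What the plan says.** Exclusion 17 in Section 6.2 bars "Prior adjuvant therapy with sorafenib or other Raf/MEK/RAS or VEGFR inhibitors", and the synopsis carries the same limit. The remaining prior-treatment rules in Sections 6.1 and 6.2 concern locoregional therapy, major surgery, interferon, rifampin and St John's wort, plus permission for earlier antivirals. None deals with sorafenib, or any other systemic anticancer drug, given earlier for advanced HCC. Section 4.2.2 adds only histological confirmation for Phase II.

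The two versions of exclusion 17 also differ. The synopsis goes on to permit *other* adjuvant therapy completed more than 6 months earlier. Section 6.2 drops the word *other*, so its second sentence can be read as readmitting remote adjuvant sorafenib.

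On the benchmark, Section 15.1 states: "The median TTP of patients with advanced HCC treated with sorafenib therapy is 5.5 months". Section 3.1 takes this from a phase III trial that randomised patients to sorafenib or placebo, and gives TTP as "5.5 months versus 2.8 months, respectively". Section 15.1 says that 38 patients allow the trial to "differentiate between a median TTP of 5.5 months and 8.3 months with 80% power". Section 15 contains no stratification, subgroup or adjustment for prior sorafenib.

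**The concern.** Phase II asks what bavituximab adds to sorafenib, and its only control is a historical number. That number must describe what the enrolled patients would do on sorafenib alone. The protocol's own rationale (Sections 3.1 and 3.3) rests on tumours escaping sorafenib. On that reasoning, a patient who has already progressed on the drug should not be expected to reach 5.5 months on it again.

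Section 3.1 calls sorafenib the standard of care. Section 7.0 recruits from medical oncology clinics anyone who meets Section 6.0, and Section 19.0 has satellite sites work from an eligibility checklist. Pretreated patients are therefore a foreseeable source of referrals, and the wording of the list decides whether they enter.

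If they do, the primary median comes from a mixture in unplanned proportions. A disappointing result could mean that bavituximab adds nothing, or that the case mix was unfavourable. With no concurrent arm and no planned split by prior exposure, the analysis could not tell these apart.

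**Working it through.** **Inputs from the documents.** Section 15.1: N = 38, medians 5.5 and 8.3 months, 80% power, two-sided 10% level, 24 months of accrual, 12 months of follow-up. Section 3.1: 2.8 months for the control group of the benchmark trial.

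**Assumptions.** The documents give neither the share of pretreated patients nor their TTP. I use shares of 10% to 30%, and an underlying median (on sorafenib alone) of 2.8 months with a range of 2.0 to 4.0. Times are exponential and accrual is uniform.

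**1. The plan's own figure.** The ratio of medians is 8.3/5.5 = 1.509. The probability of an observed event at a median of 8.3 months is O1 = 0.842. The expected count per patient under the null hazard is E0 = 0.842 × 1.509 = 1.270. The one-sample log-rank formula gives

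N = [(1.645√1.270 + 0.842√0.842) / (1.270 − 0.842)]² = 37.6, rounded up to 38.

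The stated sample size reproduces and is not in dispute.

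**2. Cohort median with a share p pretreated.** Solve for t in

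p·2^(−t/a) + (1 − p)·2^(−t/b) = 0.5,

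where a and b are the medians in pretreated and naive patients.

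- No effect: a = 2.8, b = 5.5.
- Planned effect in naive patients only: a = 2.8, b = 8.3.
- Planned effect in everyone: a = 2.8 × 1.509 = 4.23, b = 8.3.

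Check at p = 0.2 with no effect and t = 4.77: 0.061 + 0.439 = 0.500.

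**3. Power.** Section 15.1 names no test statistic. The simulation (N = 38, 40,000 trials per setting) compares the log of the exponential median estimate with 5.5 months at the two-sided 10% level; a one-sample log-rank version agrees to within 0.3 percentage points. Power is shown for the planned effect in everyone.

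| Share pretreated (median 2.8) | Median, no effect | Planned effect, none in pretreated | Planned effect in all | Power, effect in all |
|---|---|---|---|---|
| 0% | 5.50 | 8.30 | 8.30 | 75% |
| 10% | 5.12 | 7.43 | 7.73 | 64% |
| 20% | 4.77 | 6.60 | 7.20 | 51% |
| 30% | 4.44 | 5.85 | 6.70 | 37% |

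**4. Range at 20% pretreated.** With an underlying median of 2.0 months, the no-effect median is 4.44, the planned-effect median is 6.2 to 6.7, and power is 42%. With 4.0 months the figures are 5.15, 7.1 to 7.8, and 63%.

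**5. Direction.** With no effect, 20% pretreated and a median of 2.8 months, the chance of a false finding above 5.5 months falls from about 4% to about 1%. The chance of a false finding below it rises from about 6% to about 19%.

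**The case against.** The strongest reply is that this is plainly a new-start sorafenib trial. Sections 4.2.1 and 4.2.2 have sorafenib begun within 3 days of the first bavituximab dose and then titrated. Section 7.0 describes the study to patients once an initial treatment plan has been formed. The biopsy comparison group in Section 10.1 is patients beginning sorafenib monotherapy. This is good evidence of intent, and it makes a drafting slip the likeliest explanation. It does not close the gap: these passages describe dosing and recruitment, and none makes prior sorafenib a bar to entry. Exclusion 17 shows that the authors thought prior exposure needed a written rule, then confined it to the adjuvant setting.

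A second reply is that the bias is conservative. That stands, and it limits the point to false negatives and uninterpretable negatives.

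A reader might infer more than the documents support:

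- *That refractory patients were sought or enrolled.* Nothing says so; only that the list permits it.
- *That the 5.5-month figure cannot apply to pretreated patients.* The documents do not state the prior treatment of the benchmark trial's patients. Non-comparability is a reasonable inference, not an established fact.
- *That almost the whole planned effect would vanish.* This needs both a 30% share and no benefit at all in pretreated patients (5.85 months). With the same proportional benefit the median is 6.70, a loss of (8.3 − 6.7)/(8.3 − 5.5) = 57% of the planned gain. Section 3.3 hypothesises that the combination may prevent escape, so zero benefit should not be taken for granted.

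**Conclusion.** The point holds as a rule drawn too narrowly. The criteria as written admit patients treated earlier for advanced disease with sorafenib or a related inhibitor, and the plan compares them with a benchmark that probably does not describe them.

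The consequence is mainly lost power and an ambiguous negative result. At a 20% share, power falls by roughly 12 to 33 percentage points from a simulated baseline of about 75%, as the assumed underlying median runs from 4.0 down to 2.0 months. These sizes depend on an assumed share, an assumed TTP, exponential times and equal proportional benefit. If few pretreated patients enter, the effect is small. The sample size of 38 is unaffected.

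**What to change.** For Phase II, reword exclusion 17 identically in the synopsis and Section 6.2 so that it covers prior sorafenib or other Raf/MEK/RAS or VEGFR inhibitors in any setting. Extending it only to advanced or metastatic use would still leave out non-adjuvant use in earlier-stage disease. In the same amendment, reconcile the second sentence, where one version permits other adjuvant therapy and the other permits prior adjuvant therapy without that qualifier.

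If pretreated patients are to be allowed, or are already enrolled, state in Section 15.1 that the 5.5-month comparison is made in patients without prior exposure to these drugs, and report the rest separately.

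The cost is a smaller eligible pool, or a smaller primary analysis set, in proportion to the pretreated share. For example, if 20% of 38 (about 8) are set aside, 30 remain. The expected number of events is 30 × 0.842 = 25.3, and approximate power is Φ(√25.3 × ln 1.509 − 1.645) = Φ(0.42), about 66%. The same formula gives 75% for 38 naive patients. That is still better than the 51% for the mixed cohort at a 2.8-month median, and the result can be interpreted. The gain narrows if pretreated patients do nearly as well as naive ones: at 4.0 months the mixed-cohort power is 63%. If the exclusion is in place before enrolment, N stays at 38 and the only cost is slower accrual.

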7.0 RECRUITMENT PLAN

The study will be open to all patients seen at the UT Southwestern Medical Center (including Parkland Memorial Hospital System, UT Southwestern-St. Paul Hospital and the Harold C. Simmons Cancer Center), VA-North Texas, and UT Austin-Seton who meet the eligibility criteria outlined in section 6.0.

In addition, a description of the study and the enrollment criteria will be placed on the UT Southwestern Medical Center website to maximize patient recruitment. Patients will be identified from surgical, hepatology, gastroenterology and medical oncology clinics for treatment of their disease. After a discussion of the patient's disease and a formulation of the initial treatment plan, the physician-investigator will describe the study to the patient. The protocol will be discussed in a private clinic room or office. Details including the risks and obligations of the subjects will be explained. For non-English speaking patients, an independent translator will be available to communicate the details of the protocol. A research coordinator will be available either in the clinic or by phone to answer any additional questions.

Upon completion of the informed consent form and confirmation of protocol eligibility, the Clinical Research Office (CRO) at the Harold C. Simmons Cancer Center will be notified of the new enrollment. All patients will be entered into the Velos Clinical Trials Management System for ongoing monitoring.

The investigators take due notice of the NIH policy concerning inclusion of women and minorities in clinical research populations. There will be no limitation to access with regard to race or gender. Patients will be required to

read, agree to and sign an IRB-approved informed consent form prior to registration on this trial. The registration procedure will be conducted as described above. Patients will not receive payment for their participation on this study.

8.0 PRETREATMENT EVALUATION

8.1 Phase I component

To be completed within 30 +/- 3 days of starting therapy;

- CT abdomen or MRI abdomen with liver protocol
- A 12 lead electrocardiogram
- Bilateral venous duplex of lower extremities
- Documentation of all measurable or non-measurable disease parameters including radiographic imaging procedures within four weeks of study entry, and measure of biochemical marker of disease (if applicable) within four weeks of study entry. The RECIST criteria as defined by CTEP (<http://ctep.info.nih.gov/policies>) define measurable and non-measurable disease.
- Signed informed consent for study participation.

To be completed within 14 +/- 3 days of starting therapy:

- History and physical examination, including height, weight, calculated body surface area (BSA), vital signs (temperature, pulse rate, respiration rate, blood pressure), and performance status (ECOG). See Appendix A for ECOG scale.
- Serum pregnancy test for all women of childbearing potential within 14 days of starting therapy. If the test result is positive, the patient will not be allowed to participate in the study.
- Laboratory evaluation and coagulation parameters
 - CBC with differential and platelet count
 - Serum chemistries (Na, Cl, BUN, Creatinine, K, bicarbonate and glucose), albumin and calcium
 - Liver function tests (AST, ALT, alkaline phosphatase, total bilirubin),
 - Coagulation parameters (aPTT, PT and INR)
 - Urinalysis, record protein, glucose and blood
- Recording of concomitant medications

8.2 Phase II component

To be completed within 30 +/-5 days of starting therapy:

- CT or MRI abdomen with liver protocol
- A 12 lead electrocardiogram
- Biopsy (US or CT guided) of malignancy with histologic confirmation
- Bilateral venous duplex of lower extremities
- Documentation of all measurable or non-measurable disease parameters including radiographic imaging procedures within four weeks of study entry, and measure of biochemical marker of disease (if applicable) within four weeks of study entry. The RECIST criteria as defined by CTEP (<http://ctep.info.nih.gov/policies>) define measurable and non-measurable disease.
- Signed informed consent for study participation.

To be completed within 14 +/- 5 days of starting therapy:

- History and physical examination, including height, weight, calculated body surface area (BSA), vital signs (temperature, pulse rate, respiration rate, blood pressure), and performance status (ECOG). See Appendix A for ECOG scale.
- Serum pregnancy test for all women of childbearing potential within 14 days of starting therapy. If the test result is positive, the patient will not be allowed to participate in the study.
- Laboratory evaluation and coagulation parameters
 - CBC with differential and platelet count
 - Serum chemistries (Na, Cl, BUN, Creatinine, K, bicarbonate and glucose), albumin and calcium
 - Liver function tests (AST, ALT, alkaline phosphatase, total bilirubin),
 - Coagulation parameters (aPTT, PT and INR)
 - Urinalysis, record protein, glucose and blood
 - Alfa-fetoprotein
 - Viral hepatitis titers
- Recording of concomitant medications

9.0 TREATMENT/INTERVENTION PLAN

9.1 Therapy (Bavituximab and Sorafenib)

All therapy must be delivered within the UT Southwestern Medical Center and affiliates, VA-North Texas, and UT Austin-Seton.

[figure not shown]
Eligible patients with advanced HCC will receive the following:

Bavituximab: Phase I: 0.3 mg/kg, 1.0 mg/kg, or 3.0 mg/kg IV over 90 minutes weekly until disease progression or completion of 1 cycle of treatment. The dose of bavituximab will be determined by the progression of the standard 3+3 dose escalation rule explained in section 11.0.

Phase II: 0.3 mg/kg, 1.0 mg/kg, or 3.0 mg/kg IV over 90 minutes weekly until disease progression or DLT. The dose of bavituximab will be determined as the MTD from the phase I component as described in section 11.0.

Sorafenib: 200 mg PO twice a day escalating to 400 mg PO twice a day at the discretion of the treating oncologist.

A cycle constitutes 4 doses of bavituximab and 4 weeks of daily sorafenib. The treatment schema is shown below for one cycle of therapy.

Patients will be seen the day of, or within one day preceding administration of and bavituximab. An interim medical history, with particular reference to toxicities, including medication review and physical examination will be conducted at each therapy treatment visit.

A therapy treatment may be moved +/- 5 days for specific administration reasons, including clinic closure for holidays. Pre-treatment laboratory values will be captured during therapy treatment.

